4.1 Inclusion Criteria

- Adult ≥ 18 years old
- Critical care patients with small bore feeding tube inserted within last 24-48 hours
- Initial Cortrak insertion tracings: all 3 views available
- Cortrak guidewire available (these are typically saved in a plastic bag in the patient room following FT insertion).

DrIFT 2 STUDY: DISPLACEMENT IN FEEDING TUBES

Ethic/racial diversity, age, or sex are not anticipated to play a role, so our recruitment will not focus on a diverse sample.

4.2 Exclusion Criteria

- <18 years old
- Identified as “Doe”
- Unable to speak or understand English language
- Pregnancy
- Prisoners
- FT anticipated to be removed within 24 hours
- Contraindications to placing a mark on the abdomen for top foot of receiver unit (large dressings, open abdomen, halo vest, etc.)
- Original guidewire unavailable

5. Vulnerable Populations

No vulnerable populations will be targeted for enrollment but may be included except for pregnant patients and prisoners, which will be excluded.

6. Study Design

This study will use a longitudinal, repeated measures design replication study from previous pilot study.

An investigator will perform recruitment and data collection. Additional data collectors will be used as needed to ensure that data collection is performed daily, including weekends. Since this practice was safely completed in a pilot study as well as a previous study and is currently standard practice to assess tube location as needed, a waiver of written informed consent is being requested. Explanation will be provided to patients/family that we are evaluating the tube daily to assess any movement of the feeding tube.

6.1 Sample Size

The sample size of 120 participants for this study was selected based on feasibility and consultation with a biostatistician. A sample size of 120 will detect feeding tube migration over time (effect size 0.18, 80% power, alpha 0.05) using mixed effects model. The effect size was calculated by a statistician based on preliminary data from our original pilot study.

6.2 Recruitment

Investigators will review patient information daily (from census list or cortrak machine) to identify any patients in the study units with a new feeding tube placement. and will assess patient eligibility. Screening for new participants will take place for the duration of the study until the target sample size has been reached.

6.3 Data Collection

Data collection will be an ongoing process and take place every 24 hours (+/- 6 hours) following enrollment. A 6-hour window before or after the designated 24-hour data collection period was allowed for feasibility of data collection. Data collection will continue daily for the duration of the feeding tube or until Day 5. If the patient is transferred off the study unit to a medical or surgical unit at PRMC, data collection will continue. Data collection will cease at 5 days or when the feeding tube is removed.

DrIFT 2 STUDY: DISPLACEMENT IN FEEDING TUBES

6.4 Methods: PI or Sub-I

- Investigators will discuss the study with the patient or designated family member so they understand the process steps.
- Label original Cortrak* guidewire with tape ("DrIFT Study") near orange Cortrak connector port.
- Obtain insertion tracings from original feeding tube insertion.

6.4.1 Subsequent Insertions:

- Verify that original guidewire is available (see tag on proximal end).
- Position patient supine, HOB elevated 30 degrees. If unable to place supine, document position
- Connect Cortrak to guidewire. Wipe guidewire with alcohol before insertion
- Position Cortrak receiver unit on abdomen. At the time of the first data collection, a surgical marker will be used to indicate location for placement of the top foot of the receiver unit (see image attached) on the patient's abdomen. Subsequent data collection will align the top foot of receiver unit with the mark on the patient's abdomen.
- Flush FT with 30ml water per institutional protocol.
- Insert guidewire into FT and obtain Cortrak insertion tracing to determine position of distal tip of feeding tube.
- Print 3 insertion tracings (anterior, lateral, depth/cross section). Write unique identifier on the back of each tracing printout. Do not write any other information on the insertion tracing.
- Remove guidewire, wipe with alcohol and leave in bag at the bedside.
- If tubes are found to be pulled back, this will be documented along with precipitating factors. Tube will then be advanced and will continue data collection noting the change in position on data collection form.

Other study data will be entered onto a hard copy, printed data collection form and stored temporarily in the locked office of the site Sub-II. Study data will be obtained from patient observation, discussion with the nurse, and the EMR.

7. Study Duration/ Study Timeline

The proposed study will take place over a 10 month period after IRB approval. Dissemination of study findings will take place via poster or podium presentation at an appropriate conference and also published in a peer-reviewed journal.

Study Timeline

	Dec	Jan 2024	Feb	March	April	May	June	July	Aug	Sept
IRB Submission										
Recruit Participants										
Perform /Data Collection										

DrIFT 2 STUDY: DISPLACEMENT IN FEEDING TUBES

Data Analysis										
Dissemination by poster/manuscript										

8. Statistical Analysis Plan

The sample size of 120 participants for this study was selected based on feasibility and consultation with a biostatistician. A sample size of 120 will detect feeding tube migration over time (effect size 0.18, 80% power, alpha 0.05) using mixed effects model. The effect size was calculated by a statistician based on preliminary data from our original pilot study.

Bivariate descriptive characteristics of the study population will be compared according to feeding tube migration status (yes/no). Differences in patient's clinical and demographic characteristics between the groups will be assessed by chi-square statistics for categorical variables and two-sample t-tests (or Wilcoxon for nonparametric) for continuous variables.

Time to feeding tube migration will be assessed via the Kaplan-Meier (KM) method for repeated events in 24-hour blocks [11]. Patients who experience feeding tube migration may also have additional forward/backward migration in subsequent 24-hour periods. Thus, the nonparametric estimate of the survival function has to accommodate the potential for repeated events. The likelihood of feeding tube migration according to time will be obtained by the KM estimator (no migration) and cumulative distribution function (migration), respectively. Other analyses may be performed if necessary.

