8.1 Data Analysis

Data analysis will be performed using the appropriate statistical analysis software, such as IBM SPSS, SAS, etc. Descriptive statistics will be used to discuss demographics of the participants. An alpha level of 0.05 will be used to determine statistical significance for all analyses.

Outcome variable:

- Feeding tube migration (yes/no).
 - Number of hours from insertion to tube movement
 - Forward migration/backward migration
 - Zone of the FT distal tip (figure 1)

Figure 1. FT Placement/Migration Zones

Independent variables: These variables that possibly have an association with FT migration will be collected and will help to inform the design of a larger R01 study.

- Patient bedside observation
 - Date/time of data collection
 - Date/time of feeding tube insertion
 - Documentation of dual verification at initial insertion

DrIFT 2 STUDY: DISPLACEMENT IN FEEDING TUBES

- Length of feeding tube
 - Diameter of feeding tube 10 FR, 8 FR, other
 - Rate of formula ____ ml/hr
 - Bolus via FT yes/no, volume ____ ml/hr, frequency: every ____ hours
 - Cortrak device serial number
 - Length of FT inserted ____ cm
 - Mark present on abdomen for receiver unit placement? If not, apply mark using surgical marker and indicated date/time.
 - bridle present (yes/no)
 - Patient position supine/HOB elevated 30 degrees (yes/no). If no, identify position.
- EMR
 - Medical record number on enrollment form that is linked to unique study number. Do not write MRN on data collection form.
 - Was dual verification performed (yes/no).
 - Was x-ray obtained for verification (yes/no)
 - CM mark at nares at time of original insertion
 - Patient demographics
 - Sex
 - Age
 - Weight
 - Diagnosis
 - Height in cm
 - Factors that may impact motility: abdominal compartment syndrome, gastric ileus, abdominal distension, ascites or hepatic enlargement
 - Metoclopramide (yes/no)
 - Erythromycin (yes/no)
 - Vasopressors: identify by name.
 - Vomiting/retching (yes/no)
 - Excessive coughing (yes/no) ask nurse
 - Observed pulling on FT (yes/no)
 - Ambulation (yes/no)
 - Sitting on side of bed or up in chair (yes/no)
 - Prone position
 - Transfer off unit for diagnostic test/surgery or procedure (yes/no) name of test_____ date/time_____
 - Endotracheal tube removed (yes/no) date/time_____
 - Endotracheal tube replaced (yes/no) date/time_____

9. Informed Consent Process

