The primary risk for this study is microbial contamination with insertion of the stylet [12] – to mitigate this risk, the stylet will be cleaned with alcohol before every insertion. This study presents low risk level to the patients and a waiver of written informed consent is being requested.

10. Privacy and Confidentiality

Each participant will be assigned a unique study number, which will be known only to the site specific Sub-I and PI. This study number will be used to identify all data collected for the purpose of research. Data collection will be performed on printed forms by the PI or Sub-I. Data collection forms will contain only the participant's unique study number and will be de-

DrIFT 2 STUDY: DISPLACEMENT IN FEEDING TUBES

identified. Data collection forms will be stored temporarily during the data collection period in a locked office of the Sub-I. Data will then be entered into a spreadsheet on a password protected Parkview computer. Data will be maintained for a minimum of five years after the completion of the study. Only the investigators will have access to the study data.

Cortrak insertion tracings will be scanned for electronic storage. De-identified insertion tracings from each site, labeled with the file name containing unique study numbers only, will be sent to the other study site for confirmation of FT placement. Having two Sub-Is identify FT placement will increase fidelity of the study. If both Sub-Is are not in agreement regarding the zone of the distal FT tip, the other investigators on the study team (PI and Sub-I) will assess and come to consensus. Transmission of scanned insertion tracings will be sent by institutional email using the confidential setting.

An electronic file linking patient identifiers (human subjects' name, MRN, and study site) and unique study number will be kept in a file on the password protected computer of the PI. Only the principal investigator will have access to this file. The participant identification number will be kept separate from the data collected.

11. Risk/Benefit

11.1 Risk to Participants:

There are minimal risks associated with this study. Insertion of the FT guidewire and verification of FT placement using Cortrak is a standard procedure that can be performed any time that the clinician is uncertain about the position of a FT. The risk to the patient are primarily during the initial insertion, this study will only enroll patients who have the feeding tube currently in place.

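### The receiver is not aligned to a common mark between the insertion tracing and the first study tracing, so a receiver offset could create or hide apparent migration in that first interval, and no analysis separates it

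*Combined protocol and SAP*

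**What the plan says.** - **Entry.** Section 4.1 admits "Critical care patients with small bore feeding tube inserted within last 24-48 hours" and requires "Initial Cortrak insertion tracings: all 3 views available". Section 11.1 confirms that "this study will only enroll patients who have the feeding tube currently in place". No study mark can exist when the insertion tracing is made.
- **Baseline.** Section 6.4 tells investigators: "Obtain insertion tracings from original feeding tube insertion".
- **Mark.** Section 6.4.1: "At the time of the first data collection, a surgical marker will be used to indicate location for placement of the top foot". Then: "Subsequent data collection will align the top foot of receiver unit with the mark on the patient's abdomen". Section 8.1 has the mark re-applied, with date and time, if it is found missing. Section 4.2 excludes patients whose abdomen cannot be marked.
- **Landmark.** The caption to Figure 2, at the end of the document, puts the receiver's top foot at the xiphoid process.
- **Outcome.** Section 8.1 lists migration yes/no, its direction, the zone of the distal tip, and "Number of hours from insertion to tube movement". Section 8 analyses time to migration by a Kaplan-Meier method for repeated events in 24-hour blocks.

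The plan does not say whether each reading is compared with the insertion tracing or with the previous reading. It describes no analysis that treats the first interval differently from the others.

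**The concern.** The device locates the tube tip relative to a receiver resting on the abdomen. The protocol controls the receiver's position with a skin mark, checks at each visit that the mark is present, and excludes patients who cannot be marked. That control does not reach the interval from insertion to the first study reading. The supine, 30-degree position is likewise specified only for study readings, and no record of patient or receiver position at insertion is listed.

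If the receiver sat in a different place at insertion, a tube that did not move could be read in another zone, or a tube that did move could be read in the same one. The study is meant to inform how often placement should be verified, so when tubes move is a result that readers will use. As written, the analysis could not distinguish early migration from receiver offset.

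**Working it through.** **Which tracings are compared.** The time origin is insertion, the insertion tracing is collected, and the next tracing is the first study reading. The first interval therefore appears to compare those two. This is inferred, because the comparator is not stated. There are two cases:

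- Each reading compared with the previous one: only the first interval lacks a common mark, apart from intervals that span a re-mark.
- Each reading compared with insertion: every comparison uses the unmarked tracing.

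**Share of comparisons in the first case.** The pilot had 62 assessments in 20 patients, so 62/20 = 3.1 each. If the 62 exclude insertion readings (not stated), first comparisons are 20/62 = 32%. For 120 tubes that is 120 of 120 × 3.1 = 372. With five readings per tube it is 1/5 = 20%.

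**Where the first interval falls in time.** Entry is up to 48 hours after insertion. Readings are every 24 hours ± 6 following enrolment. If the first reading is at enrolment, it comes up to 48 hours after insertion. If it is one reading period later, it comes up to 48 + 30 = 78 hours after. On the time-from-insertion scale, first comparisons can therefore fall in more than one 24-hour block.

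**Size.** The plan gives no misregistration rate, so there is no figure to reproduce, and the sample-size statement does not bear on the point. Inputs: pilot rate p = 8/62 = 12.9% per assessment (Section 2) and 120 tubes (Section 4). Assumption: offset falsely changes the zone in a proportion q of tubes that did not migrate.

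- Observed first-interval rate = p + (1 − p)q = 0.129 + 0.871q
- False events = 120 × 0.871 × q
- True first-interval events = 120 × 0.129 = 15.5

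| q (assumed) | First-interval rate | False events | False share of first-interval events |
|---|---|---|---|
| 0 | 12.9% | 0 | 0 |
| 2% | 14.6% | 2.1 | 12% |
| 5% | 17.3% | 5.2 | 25% |
| 10% | 21.6% | 10.5 | 40% |

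**If offset also hides true migration.** Suppose it masks the same proportion q of true events. The rate is then p(1 − q) + (1 − p)q, which gives 14.4%, 16.6% and 20.3%. For masking to cancel the false events at q = 5%, it would have to hide 0.871 × 0.05 / 0.129 = 34% of true migrations.

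**Effect on the cumulative curve.** With five intervals at a constant, independent rate, cumulative migration is 1 − (1 − 0.129)^5 = 49.9%. Replacing the first interval by the inflated rate gives 50.9%, 52.4% and 54.9%. The distortion is more visible in timing than in the total.

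**The case against.** The strongest reply is that the first comparison is between two landmark placements. At the first reading the receiver is placed and then marked, so if both placements used the xiphoid process the offset may be small. This stands in part. The landmark should reduce the difference, but it appears only in a figure caption, and no text says the clinical insertion followed it or departed from it.

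The outcome is a zone, not a coordinate, so a small shift need not change the score. That also stands: the zone figure is not available here, and sensitivity to a shift cannot be judged. Two readers with consensus do not help, since both read the same tracings. The centimetre mark at the nares and the inserted length give a check that does not depend on the receiver, but only on external displacement. The pilot may have used the same marking procedure, in which case 12.9% already contains some artefact and adding q counts it twice. Enrolling after clinical placement makes the unmarked baseline unavoidable, although it can still be analysed separately.

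A reader might infer that every false event lands in the first 24-hour block and produces an artificial early peak. The documents do not support that, because entry up to 48 hours after insertion spreads first comparisons over more than one block, and offset may also hide events. Nor do they state that the mark was added because the landmark was thought inadequate. No reason is given.

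**Conclusion.** The point holds as a gap in alignment and analysis, not as a demonstrated bias. The insertion tracing and the first study tracing are not aligned to a common mark, and the plan has no way to separate the resulting error from true migration in that interval.

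The size is unknown. The range of 14.6% to 21.6% against 12.9% rests on the assumed q of 2% to 10%, on a pilot rate free of the same artefact, and on no masking of true events. The direction is not certain. Confining the issue to the first interval rests on reading-to-previous-reading comparison. If the comparator is always insertion, all comparisons share it. The correction is worth making because it is cheap and bears on the timing result.

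**What to change.** In Section 8:

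1. Keep the insertion-based analysis as the main analysis, and state which tracing each reading is compared with.
2. Report the insertion-to-first-reading interval separately from later intervals.
3. Prespecify a sensitivity analysis that takes the first marked tracing as reference and counts events only between tracings aligned to the same mark. Flag intervals that span a re-mark. Let each tube enter the risk set at its first marked reading, on the time-from-insertion scale.
4. Describe any early peak as migration timing only with the sensitivity result beside it.

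**Cost.** Wording in the analysis plan and one further analysis. Late entry is not part of the method now described, so some programming is needed. No tracing or patient procedure is added. At pilot follow-up the sensitivity analysis keeps 372 − 120 = 252 of 372 intervals, about one third fewer. If intervals are equally informative, confidence intervals widen by √(372/252) = 1.21, or about 20%. It drops tubes with a single reading and cannot see true migration before the first reading, so it supplements the main analysis and does not replace it.

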3.1 Secondary Objectives

1. Identify factors associated such as mobility and position changes that may affect feeding tube migration.
2. Findings may inform recommendations for clinical practice regarding the frequency for FT placement verification.
3. Validate current dual verification process for feeding tube confirmation.

4. Study Population

The sample recruited for this study will include adult patients in critical care with small bore feeding tubes (FT) in acute and critical care. All participants must be able to understand and fluently speak English.

Investigators will review patient census and data from cortrak to identify new small bore feeding tube insertions in adult patients on the designated study units and will assess eligibility criteria. We are aiming for a sample of 120 feeding tubes.

Parkview Health, Fort Wayne, IN

- Surgical trauma ICU (STICU) and Medical ICU (MICU)

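### The prompt for precipitating factors applies only to pulled-back tubes and exposure recording has no set time, so recall-based factors may be captured unequally by outcome

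*Combined protocol and SAP*

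**What the plan says.** Section 6.4.1 lists the steps of each repeat reading. One of them is "Insert guidewire into FT and obtain Cortrak insertion tracing to determine position of distal tip of feeding tube". After the tracings are printed and the guidewire is removed comes the step at issue: "If tubes are found to be pulled back, this will be documented along with precipitating factors". The section has no comparable step for a tube that has not moved or has moved forward.

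The paragraph after the list gives the sources of the remaining data: "Study data will be obtained from patient observation, discussion with the nurse, and the EMR". It does not say when in the visit the form is completed, or whether the person completing it may already know the tip position. Section 6 has an investigator do both recruitment and data collection, with extra collectors as needed.

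Section 8.1 lists the independent variables. They include pulling on the tube, vomiting or retching, ambulation, sitting or chair, prone position and transfer off the unit, and also "Excessive coughing (yes/no) ask nurse". None is conditional on movement. Section 6.3 sets the schedule: "Data collection will be an ongoing process and take place every 24 hours (+/- 6 hours) following enrollment".

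These variables serve secondary objective 1: "Identify factors associated such as mobility and position changes that may affect feeding tube migration". Section 8 compares characteristics by migration status (yes/no), with chi-square tests for categorical variables. Section 8.1 adds that the variables will inform the design of a larger study.

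**The concern.** A search for causes that starts when a tube is found displaced makes the thoroughness of exposure recording depend on the outcome. The collector at the bedside has a reason to question the nurse more closely about coughing or pulling after a displacement, and less reason when the tube is where it was. Coughing, pulling and vomiting or retching have no stated definition, threshold or look-back window, so a harder look can turn a no into a yes.

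If capture is better among migrators, a factor with no effect can appear associated with migration, and a real association can look stronger than it is. The recorded data would not show how hard anyone looked. The plan's one safeguard of this kind, two readers of de-identified tracings (section 10), protects the zone reading and not the exposure fields. At stake is the list of candidate factors carried into the larger study.

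**Working it through.** The plan states no figure on this point, so there is none to reproduce. The check has two parts.

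**1. What the sections establish together**

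- *Outcome-triggered inquiry:* yes, in 6.4.1, for pulled-back tubes only.
- *Unmoved tubes also asked:* yes. The 8.1 items are unconditional and 6.3 makes collection daily. Any difference is one of thoroughness, not of being asked or not asked.
- *Exposures recorded before the tip position is seen:* not stated either way.
- *Precipitating factors feed the analysed yes/no items:* not stated either way.

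Unequal capture is therefore possible under the plan as written, but the plan does not make it certain.

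**2. How large the distortion could be**

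Inputs:
- true exposure prevalence p = 0.20 in both groups, so the true odds ratio is 1 (assumption)
- capture s1 when prompted and s0 when not prompted, with no false positives (assumptions; the documents give none)
- share of migrators prompted f = 5/8 = 0.625, from the pilot's 5 retrograde events among 8 (section 2 background). This counts every retrograde event as a pulled-back tube, applies an event split to tubes, and assumes a pulled-back tube is classed as migrated.

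Formulas:
- capture among migrators: c1 = f × s1 + (1 − f) × s0
- recorded prevalence: a = p × c1 in migrators, b = p × s0 in non-migrators
- recorded OR = [a/(1 − a)] / [b/(1 − b)]

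For 90% vs 60%: c1 = 0.625 × 0.90 + 0.375 × 0.60 = 0.7875; a = 0.1575; b = 0.12; OR = (0.1575/0.8425)/(0.12/0.88) = 1.37.

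| s1 vs s0 | c1 | a | b | OR, f = 0.625 | OR if every migrator were prompted (f = 1) |
|---|---|---|---|---|---|
| 80% vs 70% | 0.7625 | 0.1525 | 0.14 | 1.11 | 1.17 |
| 90% vs 60% | 0.7875 | 0.1575 | 0.12 | 1.37 | 1.61 |
| 100% vs 50% | 0.8125 | 0.1625 | 0.10 | 1.75 | 2.25 |

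The effect on the chi-square test was computed exactly (uncorrected Pearson test, 120 tubes, 15, 30 or 48 migrators, prevalence 10% to 30%, true OR 1). This calculation takes f = 1, so it overstates the effect of a given gap if only pulled-back tubes are prompted.

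| Capture, migrators vs non-migrators | Recorded OR | False-positive rate at nominal 5% |
|---|---|---|
| 0.90 vs 0.90 | 1.00 | 4.2% to 5.6% |
| 0.95 vs 0.85 | 1.13 to 1.16 | 5.4% to 6.9% |
| 0.90 vs 0.70 | 1.31 to 1.39 | 7.4% to 12.1% |
| 0.90 vs 0.50 | 1.88 to 2.10 | 14% to 38% |

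With a true OR of 2, capture of 0.90 vs 0.70 gives a recorded OR of 2.60 to 2.67. Equal capture, which uniform recording aims at, leaves a null effect at 1.00.

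**The case against.** The strongest reply is that the plan already asks every tube the same questions every day. Section 8.1 carries the exposures unconditionally, and in the text as extracted most of them, including pulling, vomiting or retching and the mobility items, stand under the EMR heading; only coughing is marked for the nurse. An entry charted before the reading cannot be influenced by a tracing not yet taken. The pulled-back step can equally be read as an event note, separate from the analysed fields. The order of form and tracing is inferred from the order of the text. And the matter touches only a secondary objective meant to inform later work.

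Much of this stands. A reader might infer that unmoved tubes get no inquiry at all, or that the associations are inflated as a matter of fact. The documents support neither: the items apply to all tubes, form timing is not stated, and nothing says the prompted factors enter the yes/no fields. Nor does the prompt cover all migration, since forward movement triggers nothing extra, so figures that treat every migrator as prompted are too high.

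What the reply does not remove is the silence. Section 6.4 allows nurse discussion and bedside observation as sources alongside the EMR, and no rule separates those answers from knowledge of the tip position or from the outcome-triggered note.

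**Conclusion.** The concern holds as a risk, not as a demonstrated bias. Recall-based and observed items, clearest for coughing and also pulling and vomiting or retching, may be captured more completely for pulled-back tubes, which may push their association with migration away from the null. Items already charted with times in the EMR are less exposed. The primary objective and the Kaplan-Meier analysis do not use these variables.

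The illustrative spurious odds ratios of 1.11 to 1.75 rest on an assumed prevalence, an assumed capture gap and the pilot's split of 5 retrograde events in 8. With no gap there is no distortion. The size cannot be determined from the documents. The change is still worth making, because it is cheap and the unequal effort cannot be corrected afterwards from the recorded data.

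**What to change.** In section 6.4.1, add a step before the guidewire is connected: complete and time-stamp all section 8.1 interval exposure items (nurse questions, bedside observation, EMR) for the period since the last reading, in the same way for every tube at every 24-hour visit. Add one sentence saying that precipitating factors noted for a pulled-back tube are a separate narrative and are not used to fill or amend the analysed yes/no items.

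The cost is a reordered form and about two sentences of protocol text, with the same staff and data. There are two limits. A cause learned only after the tracing stays out of the analysed fields. And a displacement already evident from the centimetre mark, or already known to the nurse, is not masked by recording exposures first, so the change reduces the risk without removing it.

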Determine if small bore FTs migrate over time in critically ill adults receiving usual care.

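### Pulled-back tubes are advanced during follow-up with no tracing afterwards and no scoring rule, so later migration cannot be separated from the advance

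*Combined protocol and SAP*

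**What the plan says.** The primary objective (section 3) is: "Determine if small bore FTs migrate over time in critically ill adults receiving usual care".

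Section 6.4.1 describes each daily assessment. In the order listed, the guidewire is inserted, a tracing is obtained, three views are printed, and the guidewire is removed and stored at the bedside. The last item deals with pull-backs: "If tubes are found to be pulled back, this will be documented along with precipitating factors". It continues: "Tube will then be advanced and will continue data collection noting the change in position on data collection form". The sentence is passive, but it stands under the heading for methods carried out by the PI or Sub-I, so an advance by study staff is the fair reading.

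Section 8 plans a Kaplan-Meier analysis for repeated events in 24-hour blocks, on the ground that "Patients who experience feeding tube migration may also have additional forward/backward migration in subsequent 24-hour periods".

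Section 8.1 gives the outcome as migration yes/no, with "Number of hours from insertion to tube movement", "Forward migration/backward migration" and the zone of the tip. The data form also records the length of tube inserted and "CM mark at nares at time of original insertion".

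No section says whether a pull-back is a migration event, an exclusion or a censoring point. None names the reference position after an advance, and none requires a tracing at that moment.

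**The concern.** The protocol has staff move the tube tip, which is the quantity being measured, and the analysis then goes on counting movements of that tip. Two things are needed to keep the count meaningful. One is a rule for the pull-back itself. The other is a measured starting position for the interval that follows the advance. Neither is given.

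The rule could still be written later, although it would then be chosen with the data in view. The starting position could not be recovered. If no tracing is taken after the advance, the study's device next sees the tip about a day later, and that tracing shows the advance and any migration since as one displacement.

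At stake are the number, direction and timing of migration events, which are the primary result and the basis for any recommendation on how often placement should be checked.

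**Working it through.** **1. How many events can one pull-back plus advance produce?** Suppose the tube does not move by itself before the next tracing.

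| Pull-back counted? | Next tracing compared with | Events scored |
|---|---|---|
| No | Position just after the advance | 0 |
| Yes, as backward | Position just after the advance | 1 |
| No | Pulled-back tracing | 1 (false forward) |
| Yes, as backward | Pulled-back tracing | 2 (backward, then false forward) |

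If later tracings are compared with insertion instead, the answer depends on where the advance leaves the tip. A tip left in a different zone reads as migration that staff produced. The text permits every one of these rules.

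**2. Why the form entry is not enough.** Let x1 be the tip position on the pulled-back tracing, a the tip movement caused by the advance, m the movement by itself afterwards, and x2 the next tracing. Then x2 − x1 = a + m. The outcome of interest is m, so a must be known as a tip position. Section 6.4.1 asks for the change to be noted on the form but does not say in what terms. A length advanced at the nares does not by itself give the zone of the tip. A tracing after the advance measures x1 + a directly, and m follows by subtraction.

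**3. Size, as an illustration only.** The plan has no figure of its own on this point, so there is nothing to reproduce.

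Inputs:
- Pilot counts (background section): 8 migration events in 62 assessments, 5 retrograde and 3 forward. Per assessment: any p = 8/62 = 12.9%; backward b = 5/62 = 8.1%; forward f = 3/62 = 4.8%.
- Up to five daily assessments (section 6.3) on 120 tubes (section 4): at most 120 × 5 = 600 tracings.
- Pull-back rate q per day: not in the documents. Assumed 1%, 2%, 5% and 10%.

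Formulas:
- Five-day probability of any migration, pull-backs not counted: 1 − (1 − p)^5 = 1 − 0.871^5 = 49.9%.
- Pull-backs counted: 1 − [(1 − p)(1 − q)]^5. For q = 5%: 1 − (0.871 × 0.95)^5 = 61.2%.
- Backward migration: the same with b in place of p. Not counted: 1 − 0.919^5 = 34.3%.
- Forward events when each advance is scored as forward: 600f + 600q × 4/5. The 4/5 allows for pull-backs found on day 5, which have no later tracing. Without advances: 600 × 3/62 = 29.

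| Assumed q per day | Any migration, 5 days | Backward, 5 days | Forward events in 600 tracings |
|---|---|---|---|
| Not counted | 49.9% | 34.3% | 29 |
| 1% | 52.3% | 37.5% | 34 |
| 2% | 54.7% | 40.6% | 39 |
| 5% | 61.2% | 49.2% | 53 |
| 10% | 70.4% | 61.2% | 77 |

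The first two result columns show the effect of counting the pull-back. The last shows the separate effect of scoring the advance as forward migration.

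**The case against.** The strongest reply is that the events are recorded. The pull-back, its precipitating factors and the change in position all go on the form. Pulling on the tube is also collected as an independent variable. An analyst holding the form would be unlikely to score a documented advance as spontaneous forward movement. This stands in part: the last column of the table is a worst case. It does not supply the missing tip position after the advance, and it does not settle whether the pull-back counts.

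A second reply is that the documents give no pull-back rate, and at 1% per day the effect is slight. That stands. The illustration also assumes that the pilot's 8 events contained no pull-backs, which the background section does not say.

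A third reply is that taking pull-backs out of the count lowers measured displacement and could favour fewer checks. That is fair, and it is why both counts should be reported.

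Three stronger readings should not be drawn:

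- A reader might take a pulled-back tube to mean any backward shift seen on a tracing, so that staff advances would add heavily to the forward count. The protocol calls tip movement migration, reverse or retrograde. It speaks of pulling back only here, next to precipitating factors, which points to external withdrawal. All the pilot's migration events, including its 5 retrograde ones, stayed within the small bowel, and nothing says such tubes would be advanced.
- A reader might infer that staff would correct most backward migration, so that the study no longer describes usual care. This depends on the same broad reading.
- A reader might call the association between observed pulling and migration circular. Observed pulling is patient behaviour and a pull-back is a tube position. The documents do not define one by the other.

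**Conclusion.** The point holds as a gap in measurement and scoring. As written, a pulled-back tube is advanced with no tracing required afterwards, and the repeated-event analysis continues with no reference position. One such episode can be scored as zero, one or two events, and migration in the following interval is mixed with the advance.

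The size is unknown because no pull-back rate is given. The illustrative shift in five-day any-migration, 2.4 percentage points at 1% per day (52.3 − 49.9) and 20.5 at 10% (70.4 − 49.9), rests on several assumptions: the pilot rates carry over, each pilot assessment stands for one day, days are independent, pull-backs and migration are independent, all 120 tubes are followed for five days, and the pilot events included no pull-backs. The 62 pilot assessments came from 20 patients, so the base rates are themselves imprecise. The need for the fix does not depend on these figures, because the missing tracing cannot be recovered at the analysis stage.

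**What to change.** In section 6.4.1, require a new Cortrak tracing after any advance, preferably while the guidewire is still in place, and label it as a post-advance tracing. Because only the unique identifier may be written on a printout, that label needs an explicit provision there or a matching entry on the form.

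In section 8:
- record a pull-back, meaning external withdrawal shown by the inserted length, as its own event type;
- restart the interval at the advance and score later tracings against the post-advance tracing;
- never count a staff advance as forward migration;
- report migration both with and without pull-backs counted as backward events.

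The cost is a few sentences and one extra tracing per advanced tube. At the assumed rates that is at most 600 × 1% = 6 to 600 × 10% = 60 tracings over the study. Inserted length is already on the form. The statistical downside is that interval restarts at pull-backs may be informative: coughing, retching or pulling could drive both pull-backs and migration. Reporting both counts shows how far the result depends on that choice, but does not remove the problem.
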